3.2. Background

PHIs are an emerging class of agents under investigation for the treatment of anemia of CKD. These molecules stimulate erythropoiesis through inhibition of HIF-PHD enzymes (PHD1, PHD2, PHD3). This activity results in the accumulation of HIF α transcription factors which leads to increased transcription of HIF-responsive genes, stimulating components of the natural response to hypoxia. During hypoxia, PHD enzymes are inhibited, resulting in the accumulation of unhydroxylated HIF α subunits, which dimerize with HIF β subunits to affect the transcription of HIF-responsive genes, including EPO and others involved in increasing oxygen availability and utilization. Other functions regulated by HIFs include iron metabolism and utilization, angiogenesis, extracellular matrix metabolism, apoptosis, energy and glucose metabolism, vascular tone, cell adhesion, and motility (Haase, 2013).

3.3. Benefit: Risk Assessment

Summaries of findings from both clinical and non-clinical studies conducted with daprodustat can be found in the daprodustat Investigator's Brochure (IB) and IB supplement(s), if applicable.

3.3.1. Risk Assessment

The potential risks of clinical significance, including adverse events of special interest (See Section 9.2.5 for details), and the mitigation strategies for this protocol taking into account the results of completed clinical and nonclinical studies with daprodustat are outlined in [Appendix 7](#).

3.3.2. Benefit Assessment

In clinical trials of up to 24 weeks in duration, in participants with anemia of CKD, daprodustat has been shown to treat Hgb to target range. Data from prior studies with daprodustat suggest that the increases in Hgb are achieved with EPO exposure lower than those observed with rhEPO ([Holdstock, 2016](#)).

3.3.3. Overall Benefit: Risk Conclusion

Daprodustat demonstrates a positive benefit vs. risk based on the evidence as follows. In clinical trials up to 24 weeks in duration, daprodustat maintained Hgb to target range in participants with anemia of CKD (both ND and HD) with a safety profile consistent with the patient population.

This protocol employs precautions to mitigate known and potential risks to enrolled participants (see [Appendix 7](#) for details). Given these precautions, as well as the potential benefit that daprodustat holds for the treatment of anemia of CKD compared to the current standard, the overall benefit risk balance is considered to be positive.

4. OBJECTIVES AND ENDPOINTS

Objectives	Endpoints
Primary	
To compare the effect of daprodustat to darbepoetin alfa on endothelial function	
 Change in FBF ratio from Day 1 to Day 42 in response to acetylcholine
Principle Secondary	
To further compare the effect of daprodustat to darbepoetin alfa on endothelial function	
 Change in the absolute FBF from Day 1 to Day 42 in response to acetylcholine
Secondary	
To compare the effect of daprodustat to darbepoetin alfa on endothelium-independent vasodilation	
 Change in FBF ratio from Day 1 to 42 in response to sodium nitroprusside Change in the absolute FBF from Day 1 to Day 42 in response to sodium nitroprusside
To compare the effect of daprodustat to darbepoetin alfa on basal endothelial NO synthesis	
 Change in FBF ratio from Day 1 to Day 42 in response to L-NMMA Change in the absolute FBF from Day 1 to Day 42 in response to L-NMMA
To compare the effect of daprodustat on the FBF response to acetylcholine, sodium nitroprusside and L-NMMA between Day 42 and Day 1	
 Change in FBF ratio in response to each individual challenge agent at Day 42 vs Day 1 in participants treated with daprodustat Change in the absolute FBF in response to each individual challenge agent at Day 42 vs Day 1 in participants treated with daprodustat
To compare the effect of darbepoetin alfa on the FBF response to acetylcholine, sodium nitroprusside and L-NMMA between Day 42 and Day 1	
 Change in FBF ratio in response to each individual challenge agent at Day 42 vs Day 1 in participants treated with darbepoetin alfa Change in the absolute FBF in response to each individual challenge agent at Day 42 vs Day 1 in participants treated with darbepoetin alfa
To compare the effect of daprodustat to darbepoetin alfa on vascular compliance	
 Change in Augmentation Index (an indicator of arterial stiffness) as estimated by radial arterial pulse contours from Day 1 to 42 Change in pulse wave velocity (PWV) from Day 1 to Day 42
Safety	
Assess safety and tolerability	
 Incidence and severity of adverse events (AEs) and serious adverse events (SAEs) including AEs of special interest Reasons for discontinuation of randomized study treatment Absolute values and changes from baseline in clinical laboratory parameters, ECG parameters, blood pressure (BP) and heart rate (HR)

Objectives	Endpoints
Exploratory	
To explore the relationship between diabetes status and endothelial function	
 • FBF response to each individual challenge agent in relation to diabetes status

[figure not shown]
5. STUDY DESIGN

5.1. Overall Design

This study will use a randomized, repeat dose, open label, parallel group design, in adult, ND, male and female participants with anemia of CKD that are currently not treated with rhEPOs (i.e. no rhEPO use within the 12 weeks prior to the screening visit and through Day 1). The study design is outlined in [Figure 1](#).

- The study will comprise three study periods: a screening period starting up to 30 days prior to Day 1, a 42 day (6 week) treatment period with 4 visits starting at Day 1, and a follow-up visit up to 14 days later ([Figure 1](#)). The total duration of participant involvement is up to 14 weeks.
- Participants will be randomized to either daprodustat or darbepoetin alfa. A central randomization approach will be used with stratification by center.
- All participants will be treated with the goal of achieving a Hgb level within the range of 10.0 to 12.0 g/dL, consistent with national guidelines ([Medicines and Healthcare Products Regulatory Agency, 2007](#)).
- FBF and PWV will be conducted at the beginning (Day 1) and end (Day 42) of the treatment period as outlined in the SoA (See [Section 2](#)) and described in [Section 9.6](#).
- This study will include an optional, Non-Contact, Optical Forearm Plethysmography (NC-OFPP) Sub-Study (See [Appendix 8](#)).

Figure 1 Study Outline

5.2. Number of Participants

A sufficient number of participants will be enrolled such that at least 50 evaluable participants comprise the Pharmacodynamic Per-Protocol (PDPP) Population (See Section 10.3.1).

5.3. Participant and Study Completion

A participant is considered to have completed the study if he/she has completed all phases of the study including the last visit or the last scheduled procedure shown in the SoA (See Section 2).

The end of the study is defined as the date of the last visit of the last participant in the study or last scheduled procedure shown in the SoA (See Section 2) for the last participant in the trial.

5.4. Scientific Rationale for Study Design

This study will use an open label, randomized, repeat dose, parallel group design, in adult, ND, male and female participants with anemia of CKD that are currently not treated with rhEPOs (i.e., no rhEPO use within the 12 weeks prior to the screening visit and through randomization (Day 1)).

- This will be an open label study as FBF and PWV are both objective measures and not likely to be biased by the knowledge of the participant's treatment. In addition, as daprodustat is administered as an oral tablet, and darbepoetin alfa is administered subcutaneously, it would be logistically challenging to blind treatments.
- Participants will be treated for 42 days (6 weeks) with study treatment. The treatment duration was chosen to coincide with the duration of treatment where previously increases in blood pressure were observed with administration of rhEPO (Santhanam, 2010).
- The planned patient population is participants with anemia of CKD that are not on dialysis. This population was chosen as it represents a relevant population for assessing endothelial functioning as a biomarker for the potential of CV events. In addition, this population is more likely to be untreated with rhEPO, as compared to the HD population. Finally, it would not be feasible to administer therapeutic doses of daprodustat or darbepoetin alfa to participants that are not anemic due to the resulting increases in Hgb.
- The challenge agents planned to be used in this study (ACh, SNP & L-NMMA) are well-established for assessment of endothelial function by venous occlusion plethysmography (Wilkinson, 2001).

5.5. Dose Justification

The daprodustat starting dose and dose adjustment algorithm are based on dose-response longitudinal modeling of Hgb data collected across the daprodustat Phase 2 program

(GlaxoSmithKline Document Number 2015N248947_00, 2016; Holdstock, 2016). In addition, the starting (2 mg) and maintenance (1, 2 & 4 mg) doses for all participants randomized to daprodustat have been studied previously in this population and have been shown to be effective, and generally well tolerated with an AE profile consistent with that of the patient population being studied (Holdstock, 2016). Starting doses, dose steps, and elements of the dose adjustment scheme for daprodustat are provided in Section 7.1.

The darbepoetin alfa starting dose and dose adjustments are to be based on the local prescribing information as well as clinical judgement.

Dosages of the challenge agents are based on a previous study (Cheriyian, 2011). An advantage of brachial artery infusion using venous occlusion plethysmography is that most of the administered challenge agents are metabolized prior to realizing substantial systemic exposures. This is certainly the case for ACh (used to induce NO endothelial production), which is often below a physiologically active concentration once it has traversed the entire arm length, L-NMMA (used to block NO synthesis) as well as sodium nitroprusside (infused to directly induce vasodilation at the level of the smooth muscle (i.e., non-endothelial based)).

6. STUDY POPULATION

Prospective approval of protocol deviations to recruitment and enrolment criteria, also known as protocol waivers or exemptions, is not permitted.

6.1. Inclusion Criteria

Participants are eligible to be included in the study only if all of the following criteria apply:

Age

1. Participant must be at least 18 years of age inclusive, at the time of signing the informed consent.

Type of Participant and Disease Characteristics

2. Participants who are Stage 3, 4 or 5 CKD defined by eGFR using the CKD Epidemiology Collaboration (CKD-EPI) formula (Levey, 2009).
3. Hgb as measured by HemoCue at screening visit and Day 1 is ≤ 11.0 g/dL (≤ 110 g/L).
4. Palpable brachial artery as assessed at screening.
5. Participants, if necessary, may be on stable maintenance oral iron supplementation ($<50\%$ change in overall dose and compliance of 80% of prescribed doses in the 4 weeks prior to and including the screening period). If participants have been on intravenous (IV) iron, then participants will not have received IV iron for 4 weeks prior to the Day 1 visit.

Sex

6. Male or female

a. Female participants:

A female participant is eligible to participate if she is not pregnant (see [Appendix 5](#)), not breastfeeding, and at least one of the following conditions applies:

- (i) Not a woman of childbearing potential (WOCBP) as defined in [Appendix 5](#)

OR

- (ii) A WOCBP who has been on an approved form of contraceptive as defined in [Appendix 5](#) for the 4 weeks prior to Day 1 and agrees to follow the contraceptive guidance in [Appendix 5](#) until the follow-up visit.

Informed Consent

7. Capable of giving signed informed consent as described in [Appendix 3](#) which includes compliance with the requirements and restrictions listed in the informed consent form (ICF) and in this protocol.

6.2. Exclusion Criteria

Participants are excluded from the study if any of the following criteria apply:

Medical Conditions

1. On dialysis or clinical evidence of impending need to initiate dialysis within 12 weeks of Day 1.
2. Planned kidney transplant within 12 weeks of Day 1.
3. Presence of an arteriovenous (AV) fistula

Prior/Concomitant Therapy

4. rhEPO use within the 12 weeks prior to the screening visit and through Day 1.
5. History of severe allergic or anaphylactic reactions or hypersensitivity to the study treatments or challenge agents, or excipients in the study treatments or challenge agents (see daprodustat IB for list of excipients, and the Study Reference Manual (SRM) for product sheets for darbepoetin alfa and the challenge agents).
6. Planned use of any prescription or non-prescription drugs or dietary supplements that are prohibited from screening until all assessments on Day 42 have been successfully completed (see Section [7.7.2](#)).

Prior/Concurrent Clinical Study Experience

7. The participant has participated in a clinical trial and has received an experimental investigational product within the prior 30 days or within 5 half-lives of the investigational product (whichever is longer) prior to screening and through Day 1.

Diagnostic assessments

8. At or below the lower limit of the reference range at screening for Vitamin B₁₂ (may rescreen in a minimum of 8 weeks).
9. Ferritin ≤ 50 ng/mL (≤ 50 μ g/L) at screening.
10. Transferrin saturation (TSAT) $\leq 15\%$ (0.15) at screening.
11. Folate < 2.0 ng/mL (4.5 nmol/L; may rescreen in a minimum of 8 weeks) at screening.
12. High sensitivity C-reactive protein (hs-CRP) ≥ 50 μ g/mL (≥ 50 mg/L) at screening.

Other Exclusions

13. Myocardial infarction or acute coronary syndrome ≤ 12 weeks prior to screening and through Day 1.
14. Hospitalization for greater than 24 hours ≤ 12 weeks prior to screening and through Day 1.
15. Stroke or transient ischemic attack ≤ 12 weeks prior to screening and through Day 1.
16. Class IV heart failure, as defined by the New York Heart Association (NYHA) functional classification system.
17. Resting systolic blood pressure > 180 mmHg or diastolic blood pressure > 110 mmHg at screening visit or current uncontrolled hypertension as determined by the investigator.
18. QT interval corrected for heart rate using Bazett's formula (**QTcB**): QTcB > 500 msec, or QTcB > 530 msec in participants with bundle branch block. There is no QTc exclusion for participants with a predominantly ventricular paced rhythm.
19. Active chronic inflammatory disease that could impact erythropoiesis. A partial list can be found in the Study Reference Manual (SRM).
20. History of bone marrow aplasia or pure red cell aplasia.
21. Conditions, other than anemia of CKD, which can affect erythropoiesis. A partial list can be found in the SRM.
22. Evidence of actively bleeding gastric, duodenal, or esophageal ulcer disease OR clinically significant GI bleeding from ≤ 8 weeks prior to screening and through Day 1.
23. Liver disease (any of the following):
 - Alanine transaminase (ALT) $> 2x$ upper limit of normal (ULN; screening only)
 - Bilirubin $> 1.5x$ ULN (screening only)
NOTE: Isolated bilirubin $> 1.5 x$ ULN is acceptable if bilirubin is fractionated and direct bilirubin $< 35\%$
 - Current or chronic history of liver disease, or known hepatic or biliary abnormalities (with the exception of Gilbert's syndrome or asymptomatic gallstones).

24. Major surgery within the 12 weeks prior to screening and through Day 1, or planned during the study.
25. Anticipated or planned vascular access surgery (i.e., AV fistula) within the 12 weeks prior to screening and through the Day 42 assessments.
26. Received a tissue heart valve replacement or repair within the 6 months prior to screening or has received a mechanical heart valve replacement.
27. Blood transfusion within 6 weeks prior to screening and through Day 1, or an anticipated need for blood transfusion during the study.
28. Clinical evidence of an acute infection, or history of infection requiring IV antibiotic therapy from 8 weeks prior to screening and through Day 1.
NOTE: Prophylactic oral antibiotics are allowed.
29. History of malignancy within the two years prior to screening and through Day 1 or currently receiving treatment for cancer, with the exception of localized squamous cell or basal cell carcinoma of the skin definitively treated 12 weeks prior to Day 1.
30. Platelet count < 50,000/ μ L.(<50 GI/L)
31. History of a bleeding disorder (e.g., hemophilia).
32. Any other condition, clinical or laboratory abnormality, or examination finding that the investigator considers would put the participant at unacceptable risk, which may affect study compliance or prevent understanding of the aims or investigational procedures or possible consequences of the study.

6.3. Lifestyle Restrictions

6.3.1. Meals and Dietary Restrictions

Apart from a light breakfast (e.g., plain toast) and clear water which is allowed, participants are to refrain from any other food and drink for at least 8 h prior to the venous occlusion plethysmography performed on Days 1 and 42.

6.3.2. Caffeine, Alcohol and Tobacco

- Participants will be instructed to avoid caffeine/xanthine-containing products (i.e., coffee, tea, cola drinks, chocolate) for 6 hours prior to the venous occlusion plethysmography performed on Days 1 and 42.
- Participants will be instructed to avoid alcohol for 24 h prior to the venous occlusion plethysmography performed on Days 1 and 42.
- Participants will be instructed to avoid the use of nicotine and/or nicotine containing products for 24 h prior to the venous occlusion plethysmography performed on Days 1 and 42.

6.3.3. Activity

Participants will refrain from strenuous exercise for 24 h prior to the venous occlusion plethysmography performed on Days 1 and 42.

6.4. Screen Failures

Screen failures are defined as participants who consent to participate in the clinical study but are not subsequently randomized. A minimal set of screen failure information is required to ensure transparent reporting of screen failure participants to meet the Consolidated Standards of Reporting Trials (CONSORT) publishing requirements and to respond to queries from regulatory authorities. Minimal information includes demography, screen failure details, eligibility criteria, and any SAEs.

Participants that fail screening are eligible to be rescreened up to an additional 2 times as soon as the investigator assesses (or 8 weeks later if low vitamin B₁₂) they may meet study entry criteria. If participants are rescreened, they must sign a new informed consent form.

7. TREATMENTS

Study treatment is defined as any investigational treatment(s), marketed product(s), placebo, or medical device(s) intended to be administered to a study participant according to the study protocol. Eligible participants will be randomized to receive **either** daprodustat or darbepoetin alfa.

Participants randomized to daprodustat will receive this study treatment daily, starting Day 1 through Day 41 (i.e., day prior to FBF & PWV procedures). Participants randomized to darbepoetin alfa will receive this study treatment every 2 weeks, starting Day 1 through Day 28.

7.1. Treatments Administered

Study Treatment Name:	Daprodustat	Darbepoetin alfa (Aranesp)
Dosage formulation:	Tablet	Solution for injection
Unit dose strength(s)/ Dosage level(s):	1 mg, 2 mg, 4 mg tablet strengths/1 mg, 2 mg, 4 mg dosage levels	Darbepoetin alfa is commercially available in various single-dose vials and single-dose prefilled syringes
Route of Administration	Oral	Subcutaneous injection
Dosing instructions:	1 tablet to be taken daily without regard for food	Administered subcutaneously every 2 weeks as per product labelling
Packaging and Labeling	Study Treatment will be provided in a bottle. Each bottle will be labeled as per country requirement.	As per commercial packaging and product labelling
Manufacturer	GlaxoSmithKline (GSK)	Amgen

7.1.1. Study Treatments

7.1.1.1. Daprodustat Dosing Information

Daprodustat will be administered orally once daily starting **after** the completion of the FBF & PWV procedures on Day 1. The only exception to this is if a Repeat Day 1 is necessary (See Section [9.6.1.4](#)).

Daprodustat Starting Dose

[figure not shown]
All participants randomized to the daprodustat group will be dosed with 2 mg orally once daily starting on Day 1 (See Section 5.5)

Daprodustat Dose Adjustment Algorithm

Participants randomized to daprodustat will have doses adjusted, as required, to target Hgb within the range of 10.0 to 12.0 g/dL. Dose adjustments will be assigned **automatically** via the IWRS (Interactive Web Response System) based on the participant's Hgb value via onsite HemoCue assessment according to the algorithm in Table 1 on Day 28 as noted in the SoA (See Section 2).

The available dose steps for daprodustat are outlined in Figure 2 (highlighted box indicates starting dose). Dose adjustments will result in the daprodustat dose being increased or decreased by **one dose step (up or down) at a time**.

Figure 2 Daprodustat Dose Steps

7.1.1.2. Darbepoetin Alfa Dosing Information

Darbepoetin alfa will be administered subcutaneously (SC) once every two weeks starting **after** the completion of the FBF & PWV procedures on Day 1.

Darbepoetin Alfa Starting Dose and Dose Adjustments

Participants randomized to darbepoetin alfa will receive study treatment according to local labelling, clinical practice guidelines, and clinical judgement to maintain Hgb in the target range (10.0-12.0 g/dL). For additional guidance on Hgb-based stopping criteria please refer to Section 8.1.2. Darbepoetin alfa is to be administered as a single subcutaneous injection once every two weeks as outlined in the SoA (See Section 2), although doses can be temporarily held or delayed if necessary to maintain patient safety (after consultation with the study medical monitor). Doses can only be modified on Day 28 as noted in the SoA (See Section 2).

7.1.2. Challenge Agents

The use of these challenge agents is described on the assumption they are available for both visits for an individual participant. If either of the secondary challenge agents (SNP and L-NMMA) are unavailable then that agent will be excluded from the procedure for that individual participant. If, for any reason, both SNP and L-NMMA become unavailable, the participant will receive ACh only.

All of the challenge agents will be infused in a fixed order (See Section 9.6.1, Figure 4) into the brachial artery, preferably the brachial artery of the nondominant (test) arm via a 27-gauge needle inserted under local anesthesia. All challenge agents will be prepared

aseptically and diluted in sterile saline (0.9%). All infusions will be performed at a rate of 1 mL/min.

7.1.2.1. Acetylcholine Dosing Information

Endothelial function will be assessed by determining the vasodilator response to acetylcholine. Acetylcholine will be infused at 7.5, 15 & 30 µg/min each for 6 min per infusion into the brachial artery of the test arm.

7.1.2.2. Sodium Nitroprusside Dosing Information

Measurement of endothelium-independent vasodilation will be with sodium nitroprusside. Sodium nitroprusside will be infused at 3 and 10 µg/min each for 6 min per infusion into the brachial artery of the test arm.

7.1.2.3. L-N^G-monomethyl Arginine Acetate (L-NMMA) Dosing Information

The effects of daprodustat or darbepoetin alfa on basal NO synthesis will be assessed using L-NMMA at a doses of 2 and 8 µmol/min for 6 min each per infusion into the brachial artery of the test arm.

7.2. Dose Modification

Doses of daprodustat can be modified on Day 28 based on the participant's Hgb level as measured using the HemoCue device. The dose modifications, based on the Hgb value and change from previous measurement, are found in [Table 1](#).

Doses of darbepoetin alfa can be modified on Day 28 based on the participant's Hgb level as measured using the HemoCue device based on local product labelling, clinical practice guidelines, and clinical judgement.

Table 1 Daprodustat Dose Modification Algorithm

Hgb (g/dL)	Hgb change since Day 1 visit	Dose Adjustment
< 7.5	Any change	Repeat HemoCue assessment on the same sample at same study visit to confirm; take average of 2 values. If confirmed, permanently discontinue study treatment and withdraw subject from the study (See Section 8.1.2).
≥7.5 to < 10.0	Decreasing or No change (i.e., < 0.5 g/dL increase)	Increase to the next higher dose step
≥7.5 to < 10.0	Increasing by at least 0.5 g/dL	Maintain dose
≥10.0 to ≤ 12.5	Any change	Maintain dose
> 12.5 to < 13.0	Increasing or No change	Decrease to the next lower dose step
	Decreasing	Maintain dose

Hgb (g/dL)	Hgb change since Day 1 visit	Dose Adjustment
≥13.0	Any change	Repeat HemoCue assessment on the same sample at same study visit to confirm; take average of 2 values. If confirmed, permanently discontinue study treatment and withdraw subject from the study (See Section 8.1.2).
≥7.5 - <13.0	≥1.3 g/dL increase in Hgb over the previous 2 weeks (as assessed on Day 28 only) ¹	Repeat HemoCue assessment on the same sample at same study visit to confirm; take average of 2 values. If confirmed, decrease to next lower dose step (see Section 7.1.1)
≥7.5 - <13.0	>2 g/dL increase in Hgb over the previous 4 weeks.	Repeat HemoCue assessment on the same sample at same study visit to confirm; take average of 2 values. If confirmed, decrease to next lower dose step (see Section 7.1.1)

¹ If increase in Hgb >1.3 g/dL is noted on Day 15, please refer to Hgb Stopping Criteria Table below (Section 8.1.2).

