8.1.2. Hgb Stopping Criteria

GSK will supply a point-of-care Hgb analyzer (HemoCue) to each site for rapid and convenient monitoring of Hgb levels and to ensure consistency of Hgb measurements across sites participating in the study.

Blood samples for measurement of Hgb concentrations via HemoCue will be collected and recorded in the eCRF. [Table 2](#) summarizes the Hgb values and corresponding action to be taken at each visit.

Table 2 Hgb Stopping Criteria

Hgb (g/dL) at visit		Action
<7.5		Repeat HemoCue assessment on the same sample at same study visit to confirm; take average of 2 values. If confirmed, permanently discontinue study treatment and withdraw participant from the study.
≥7.5 - <13.0 with:	≥2.0 g/dL decrease in Hgb over the previous 2 weeks	Repeat HemoCue assessment on the same sample at same study visit to confirm; take average of 2 values. If confirmed, permanently discontinue study treatment and withdraw participant from the study.
≥7.5 - <13.0 with:	≥1.3 g/dL increase in Hgb over the previous 2 weeks (at Day 15 only) ¹	Repeat HemoCue assessment on the same sample at same study visit to confirm; take average of 2 values. If confirmed, permanently discontinue study treatment and withdraw participant from the study.
≥13.0		Repeat HemoCue assessment on the same sample at same study visit to confirm; take average of 2 values. If confirmed, permanently discontinue study treatment and withdraw participant from the study.

¹ If increase in Hgb >1.3 g/dL is noted on Day 28, refer to Dose Modification (Section 7.2).

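### Table 1 gives conflicting Day 28 daprodustat doses for the same Hgb values, and Table 2's early rapid-rise stop is tied to a day that is not a scheduled visit

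*Protocol*

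**What the plan says.** **Reference visit.** The text of Protocol Section 7.2 describes "The dose modifications, based on the Hgb value and change from previous measurement". The Table 1 column that holds the change criterion is headed "Hgb change since Day 1 visit".

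**Base rows of Table 1.**
- From 7.5 to below 10.0 g/dL, the dose goes up one step under "Decreasing or No change (i.e., < 0.5 g/dL increase") and is kept if Hgb has risen by 0.5 g/dL or more.
- In the row "≥10.0 to ≤ 12.5" it is kept whatever the change.
- In the row "> 12.5 to < 13.0" it goes down if Hgb is rising or unchanged and is kept if Hgb is falling.

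**Rapid-rise rows of Table 1.** Two further rows cover 7.5 to below 13.0 g/dL and lower the dose one step if a repeat reading confirms. One requires "≥1.3 g/dL increase in Hgb over the previous 2 weeks (as assessed on Day 28 only"), the other a rise of more than 2 g/dL over four weeks.

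**Application.** Section 7.1.1.1 has the IWRS assign the Day 28 dose automatically from Table 1. The table governs daprodustat only.

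**Early stop.** Table 2 (Section 8.1.2) withdraws a participant with a confirmed "≥1.3 g/dL increase in Hgb over the previous 2 weeks (at Day 15 only"). The Table 1 footnote reads "If increase in Hgb >1.3 g/dL is noted on Day 15, please refer to Hgb Stopping Criteria Table below". The Schedule of Activities (Section 2) has a HemoCue visit at Day 14, ±2 days, and none labelled Day 15. Table 2 applies to both arms; Section 7.1.1.2 refers darbepoetin participants to Section 8.1.2.

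**The concern.** A table that drives automatic dosing must return one action for each set of readings. Here the lead-in and the column heading compare the Day 28 value with different visits, and the rapid-rise rows cut across the base rows with no stated order. Two people programming Table 1 in good faith could assign different doses to the same participant.

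The visit label matters for a different reason. Under Section 8.1 a participant who stops treatment is withdrawn. That participant has no Day 42 FBF and falls outside the Pharmacodynamic Per-Protocol (PDPP) population, which carries the primary analysis. Whether the early rapid-rise rule covers the whole visit or one calendar day therefore decides who can contribute data.

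The risk table in Appendix 7 cites Sections 7.2 and 8.1 as mitigation for excessive erythropoiesis, and SAP Section 2.3 says the dosing algorithm exists to keep treatment consistent across the study. Both rely on the rules having one reading.

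**Working it through.** The plan states no figure on this point to reproduce. The check applies Tables 1 and 2 literally to Hgb values in g/dL.

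**Inputs.** Day 1 Hgb is at most 11.0 (Section 6.1, criterion 3). The Day 14 visit has a ±2 day window (Section 2). The start dose is 2 mg and the other doses are 1 and 4 mg (Section 5.5). The row limits are those of Tables 1 and 2. The repeat reading is assumed to confirm the first.

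**Step 1: single participants at Day 28.**

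| Case | Day 1 / 14 / 28 | Base row, change since Day 1 | Base row, change since Day 14 | Rapid-rise row |
|---|---|---|---|---|
| A | 9.0 / 9.6 / 9.7 | 9.7 − 9.0 = +0.7: maintain | 9.7 − 9.6 = +0.1: increase | not met |
| B | 9.5 / 10.0 / 11.5 | maintain (any change) | maintain (any change) | 11.5 − 10.0 = +1.5 in 2 weeks: decrease |
| C | 9.5 / 8.3 / 9.7 | 9.7 − 9.5 = +0.2: increase | 9.7 − 8.3 = +1.4: maintain | +1.4 in 2 weeks: decrease |

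In case C the Day 14 fall is 9.5 − 8.3 = 1.2, below the 2.0 stopping limit, so the participant is still on treatment. The three actions give 4, 2 or 1 mg.

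**Step 2: how widely the rules conflict.** All combinations in 0.1 steps were listed, with Day 1 from 7.5 to 11.0 and Days 14 and 28 from 7.5 to 12.9. Combinations stopped by Table 2 were removed: a rise of at least 1.3 or a fall of at least 2.0 at the Day 14 visit, or a fall of at least 2.0 at Day 28. This leaves 48,850.
- The base-row action depends on the reference visit in 3,924. In 2,650 the Day 1 reference gives increase and the Day 14 reference gives maintain; in 1,274 it is the reverse. All have Day 28 Hgb below 10.0.
- With the base rows read by the column heading, 23,311 combinations also meet a rapid-rise row, which says decrease. The base row says maintain in 18,981, increase in 572 and decrease in 3,758 (18,981 + 572 + 3,758 = 23,311). The conflict covers 18,981 + 572 = 19,553.

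These are counts of possible values, not probabilities for patients.

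**Step 3: the row above 12.5 with falling Hgb.**
- By the column heading, the smallest possible change is 12.6 − 11.0 = +1.6, so Hgb cannot have fallen since Day 1. No sequence reaches the row.
- By the lead-in, Day 14 must be at least 12.7, a rise of at least 12.7 − 11.0 = 1.7. Table 2 withdraws that participant if its early rule covers the Day 14 visit, so again no sequence reaches the row.
- The row can be reached, for example by 11.0/12.9/12.7, only by the lead-in and with the early rule confined to calendar Day 15.

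Choosing one reference visit therefore does not by itself make the whole table coherent.

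**Step 4: Day 14 against Day 15.** The window runs from Day 12 to Day 16, so Day 15 is one of five permitted days. Take a rise from 9.5 to 10.9 (+1.4) at a visit held on Day 14. If Day 15 names the visit, the participant is withdrawn. If it names the calendar day, there is no stopping action.

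**Step 5: the threshold.** Both operative rows use ≥1.3; the footnotes to both tables use >1.3. A rise of exactly 1.3 meets the rows but not the footnotes.

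**The case against.** The strongest reply is that the intended reading can be worked out:
- **Reference visit.** Sections 7.2 and 7.1.1.1 both point to Table 1 as the algorithm, so its heading could be taken to outrank an introductory sentence. The IWRS must also implement a single reading, which limits variation between sites.
- **Overlap.** If the base rows prevailed, the rapid-rise rows would do almost nothing. The Table 2 footnote sends a Day 28 rapid rise to Section 7.2, and the amendment summary says such participants may have the dose decreased. On that inference, cases B and C each have one outcome.
- **Day 15.** Table 2 is framed by visit, and only one HemoCue visit lies between Day 1 and Day 28. The SAP study-day formula (Section 10.6.1) puts a reading 14 days after first dose on Study Day 15, which may explain the label.
- **Consequences.** An unreachable row changes nobody's dose, and the footnotes set no action.

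Much of this stands as a limit on weight. Misdosing cannot be shown, since the IWRS specification is not in the documents. The Day 15 wording is ambiguous rather than unworkable, and the threshold mismatch is minor. But no operative passage states a precedence. The amendment summary is not operative text, and an automated algorithm cannot rest on inference. The study-day explanation does not fit the Day 28 label, because 28 days after first dose would be Study Day 29. The contradiction over the reference visit remains in the current text.

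**Conclusion.** The concern holds. As written, Section 7.2 and Table 1 return different Day 28 daprodustat actions for the same readings, in the extreme all three possible actions. Table 2's early rapid-rise withdrawal has two readings.

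The scope is limited. The reference-visit and overlap problems affect only the Day 28 daprodustat dose and withdraw nobody. Only the visit label bears on withdrawal. The checks are logical, use scheduled readings and assume the repeat reading confirms. The documents give no data on how often such cases arise, and no loss of power or arm-related data loss is claimed.

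The effect on the reported results is small: SAP Section 2.1 records termination with 4 completed subjects and summary statistics only. The point should be fixed, but it does not threaten the conclusions.

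**What to change.** The sponsor's medical team should reconcile the passages:
- use one reference visit in the Section 7.2 text and the Table 1 heading;
- make the Table 1 rows mutually exclusive, or state which takes precedence;
- use the scheduled visit label in Tables 1 and 2 and their footnotes;
- use one inequality for 1.3 g/dL;
- confirm that each row can be reached by a participant who meets inclusion criterion 3.

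The IWRS specification should then be checked against the reconciled table. For the terminated study, the report should state which reading was applied at Day 14 and at Day 28.

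The cost is protocol wording, one specification check and one sentence in the report, with no new data or visits. The choice of dose and clinical rule is left to the sponsor.
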